### **6.1.3 Exploratory Efficacy Endpoints**

For the exploratory efficacy endpoints of proportion of events, subjects whose status of events are unknown due to, e.g., missing data will not be counted as the events, unless specifically stated otherwise.

1. All-cause mortality at day 30 (Visit 9)
2. All-cause mortality at day 90 (Visit 10)
3. Number of subjects needing RRT at day 30 (Visit 9)
4. Number of subjects needing RRT at day 90 (Visit 10)
5. Number of subjects with  $\geq 25\%$  sustained reduction in eGFR based on SCr at day 30 (Visit 9)
6. Number of subjects with  $\geq 25\%$  sustained reduction in eGFR based on SCr at day 90 (Visit 10)
7. Proportion of subjects with MAKE defined as all-cause mortality, RRT and/or  $\geq 25\%$  sustained reduction in eGFR based on cystatin-C within 30 days after day of surgery (MAKE30 with eGFR based on cystatin-C).
  - If the subject meets at least one of the following conditions by day 30 (Visit 9), then the subject will be treated as with MAKE30 with eGFR based on cystatin-C.
    - All-cause mortality;
    - Initiation of RRT; and/or,
    - eGFR based on cystatin-C at day 30 (Visit 9) equal to or less than 75% of the baseline value.
8. Proportion of subjects with MAKE defined as all-cause mortality, RRT and/or  $\geq 25\%$  sustained reduction in eGFR based on cystatin-C within 90 days after day of surgery (MAKE90 with eGFR based on cystatin-C).
  - If the subject meets at least one of the following conditions by day 90 (Visit 10), then the subject will be treated as with MAKE90 with eGFR based on cystatin-C.
    - All-cause mortality;
    - Initiation of RRT; and/or,
    - eGFR based on cystatin-C at day 90 (Visit 10) equal to or less than 75% of the baseline value.
9. Number of subjects with  $\geq 25\%$  sustained reduction in eGFR based on cystatin-C at day 30 (Visit 9)
10. Number of subjects with  $\geq 25\%$  sustained reduction in eGFR based on cystatin-C at day 90 (Visit 10)
11. Number of hospital days during initial hospitalization
  - The number of hospital days per subject during initial hospitalization will be calculated as: Date of discharge – Date of admission + 1 (for the initial hospitalization including ICU).
    - Initial hospitalization is a hospitalization which includes the day of surgery
    - If the date of admission of a hospitalization record is the same as the date of discharge of the previous record, for example because two records are created to

illustrate that the subject is moved from one hospital to another hospital or from a standard care to ICU, then the two records will be combined into one record.

- If the hospitalization is ongoing at the end of study, the date of discharge is replaced by the last date of completed or discontinued recorded in eCRF period status forms.

12. Number of ICU days during initial hospitalization

- The number of ICU days per subject during initial hospitalization will be calculated as: Date of discharge – Date of admission + 1 (for the initial ICU hospitalization).
- Initial hospitalization is a hospitalization which includes the day of surgery
- If the hospitalization is ongoing at the end of study, the date of discharge is replaced by the last date of completed or discontinued recorded in eCRF period status forms.

13. Total number of hospital days up to day 90

- The number of hospital days per subject up to day 90 will be calculated as: Sum of the durations of all hospitalizations including ICU in days (Date of discharge – Date of admission + 1).
- Initial hospitalization and all subsequently hospitalizations are included. Initial hospitalization is a hospitalization which includes the day of surgery
- If the date of admission of a hospitalization record is the same as the date of discharge of the previous record, then the two records will be combined in one record.
- If the hospitalization is ongoing at the end of study, the date of discharge is replaced by the last date of completed or discontinued recorded in eCRF period status forms.

14. Total number of ICU days up to day 90

- The number of hospital days per subject up to day 90 will be calculated as: Sum of the durations of all ICU in days (Date of discharge – Date of admission + 1).
- Initial hospitalization and all subsequently hospitalizations are included. Initial hospitalization is a hospitalization which includes the day of surgery
- If the hospitalization is ongoing at the end of study, the date of discharge is replaced by the last date of completed or discontinued recorded in eCRF period status forms.

15. Alternative derivations of proportion of subjects developing AKI using different definitions [[Table 3](#)] within 72 hours after T0.

- All stages AKI-UO (AKI-UO stage 2 or stage 3)
- AKI-UO stage 3
- AKI-SCr stage 2 or 3
- AKI-SCr stage 2 or 3 and/or AKI-UO stage 3
- AKI based on S-cystatin-C, defined as an increase of  $\geq 10\%$  of baseline serum cystatin-C [KDIGO, 2012]
- AKI based on S-cystatin-C, defined as an increase of  $\geq 25\%$  of baseline serum cystatin-C

**Table 3 Definitions of Stages**

Stage	AKI-SCr	AKI-UO
1	$\geq 1.5$ to $< 2$ times baseline, or Increasing $\geq 0.3$ mg/dL within any 48 hours	(Not used for this study)
2	$\geq 2$ to $< 3$ times baseline	$< 0.5$ mL/kg per hour for over 12 hours
3	$\geq 3$ times baseline, Increase in serum creatinine to $\geq 4.0$ mg/dL, or Initiation of RRT	$< 0.3$ mL/kg per hour for over 24 hours, or Anuria for over 12 hours

AKI-SCr: acute kidney injury based on serum creatinine KDIGO criteria; AKI-UO: acute kidney injury based on urinary output; RRT: renal replacement therapy

KDIGO Clinical Practice Guideline for Acute Kidney Injury. Official Journal of the International Society of Nephrology: Kidney International Supplements. 2012;2(1):1-138.

16. Alternative derivations of proportion of subjects developing AKI using different definitions [Table 3] within 7 days after T0.
17. Proportion of subjects developing AKI (any stage) based on SCr criteria from the KDIGO guideline within 5 days after T0 (i.e., until Visit 6) (AKI-SCr5d).  
[SCr evaluation visit: baseline, Visit 3, 4, 5 and 6 (24 hours, 48 hours, 72 hours after T0, and Day 5). If the hospital discharge is earlier than Day 5, then the visits prior to DoD and Visit 8 (DoD) will be used.]
  - If the subject meets at least one of the following conditions, then the subject will be treated as developing AKI-SCr5d.
    - Increasing in SCr  $\geq 0.3$  mg/dL within any 48 hours until Visit 6; and/or,
    - Increasing in SCr  $\geq 1.5$  times baseline until Visit 6.
18. Proportion of subjects developing AKI based on all criteria from the KDIGO guideline within 5 days after T0 (AKI-KDIGO5d).  
[SCr evaluation visit: baseline, Visit 3, 4, 5 and 6 (24 hours, 48 hours, 72 hours after T0, and Day 5). If the hospital discharge is earlier than Day 5, then the visits prior to DoD and Visit 8 (DoD) will be used.]  
[UO evaluation visit: Visit 3, 4, 5 and 6 (0-12 hours, 12-24 hours, 0-24 hours, ..., and 72-84 hours, 84-96 hours and 72-96 hours after T0). If the hospital discharge is earlier than Day 5, then the visits prior to DoD and Visit 8 (DoD) will be used.]
  - If the subject meets at least one of the following conditions, then the subject will be treated as developing AKI-KDIGO5d.
    - Increasing in SCr  $\geq 0.3$  mg/dL within any 48 hours until Visit 6;
    - Increasing in SCr  $\geq 1.5$  times baseline until Visit 6; and/or,
    - Urine volume  $< 0.5$  ml/kg per hour for any one of 12 consecutive hours until Visit 6 (i.e., 0-12 hours after T0, 12-24 hours after T0, ..., or 84-96 hours after T0).
19. Severity of AKI within 72 hours after T0
  - Severity of AKI based on AKI-SCr stages (Stage 1, 2, 3 or no AKI. No AKI means subject not developing AKI-SCr72h.)

- Severity of AKI based on AKI-UO stages (Stage 2, 3, or no AKI. No AKI means subject not developing AKI-UO)
- Severity of AKI based on most severe of AKI-SCr or AKI-UO stages (Stage 1, 2, 3 or no AKI)

20. Severity of AKI (based on AKI stage using SCr and/or UO) within 7 days after T0

21. Duration of AKI based on AKI stage using SCr

- Duration of AKI-SCr72h: time from moment of first meeting criteria for AKI-SCr72h until moment of first not meeting the criteria for AKI-SCr72h, death or hospital discharge. If the duration of AKI-SCr72h exceeds day 7 the time of ending of AKI will be assessed retrospectively on day 30 (visit 9) based on local SCr laboratory results. The date and value when respective criteria of AKI-SCr72h were resolved is recorded in the eCRF as an unscheduled event with check of “First NOT meeting the criteria for AKI-SCr72h/7d (SCr  $\geq$ 1.5 times baseline) before hospital discharge, if the duration of AKI-SCr72h/7d exceeds Visit 8 (Day 7).”.
- The duration will be calculated as follows;  
(Date of first not meeting the criteria, death or hospital discharge – Date of first meeting the criteria) in days.  
For subjects who don't occur AKI-SCr72h, the duration of AKI will be treated as 0.
- Duration of AKI-SCr7d (definition as above)

22. Time to AKI-SCr72h (i.e., the time from T0 to the time when criteria for AKI-SCr72h are met). The time to AKI-SCr72h will be calculated as: (Date of first meeting the criteria – Date of T0 + 1) in days.

23. Time to AKI-SCr7d (definition as above)

24. Proportion of subjects with AKI as defined by a 50% or higher reduction in eGFR based on the cystatin-C equation within 72 hours after T0.

- If the subject meet the following condition, then the subject will be treated as with AKI for this endpoint.
  - At least one of eGFR based on cystatin-C equation within 72 hours after T0  $\leq$  50% of the baseline value.

25. Proportion of subjects with AKI as defined by a 50% or higher reduction in eGFR based on the cystatin-C equation within 7 days after T0.

- If the subject meet the following condition, then the subject will be treated as with AKI for this endpoint.
  - At least one of eGFR based on cystatin-C equation within 7 days after T0  $\leq$  50% of the baseline value.

26. Proportion of subjects that have a reduction of NC AKIRisk score 24 hours after T0 (visit 3) to or below  $0.3 \text{ (ng/ml)}^2/1000$

27. Proportion of subjects with renal recovery, defined as a SCr value at hospital discharge equal to or lower than that at baseline

- SCr value at hospital discharge is defined as follows;

- If the hospital discharge is at or before day 7, the value at Visit 8 will be used.
- If the hospital discharge is after day 7, the value recorded as unscheduled event with check of “Last SCr value before hospital discharge.” will be used.

28. Time to ventilator weaning, defined as the time from T0 to extubation (i.e., removal of the endotracheal ventilation tube)

- Time to ventilator weaning is defined as: (Date and time of Extubation for the first record in “Mechanical Ventilation” form in eCRF – Date and time of T0) in hours.

29. Acute physiology and chronic health evaluation II (APACHE-II) up to day 4 (if the subject is on the ICU)

30. Number of readmissions to ICU

31. Number of readmissions to hospital

- All readmissions after initial hospitalization are included. Initial hospitalization is a hospitalization which includes the day of surgery
- If the date of admission of a hospitalization record is the same as the date of discharge of the previous record, then the two records will be combined into one record.

32. Changes from baseline in SCr, S-cystatin-C, eGFR based on SCr and Cystatin-C, and other biomarkers in blood and urine through 72 hours after T0

33. Area under the curve of SCr and S-cystatin-C through 72 hours after T0 (AUCSCr72h and AUCSCysC72h)

- AUCSCr72h is defined by Linear Trapezoidal Method as below;  
$$\text{AUCSCr72h (mg/dL*day)} = \text{sum of } (SCr_i + SCr_{i+1}) \times (Time_{i+1} - Time_i) / 2$$
where i=Visit 2 to 4
- AUCSCysC72h is defined in the same way as above.
- In the case of missing at 72 hours after T0, the missing value will be imputed from the last available value using Last Observation Carried Forward.

34. Area under the curve of SCr and S-cystatin-C through day 7 after T0(AUCSCr7d and AUCSCysC7d)

- AUCSCr7d and AUCSCysC7d are defined based on all available values through day 7 after T0 in the same way as AUCSCr72h and AUCSCysC72h

35. 5-level European Quality of Life 5 Dimensions Questionnaire (EQ-5D-5L) on baseline, visit 8, day 30 and day 90

- EQ-5D 5L includes two main components: (1) a Visual Analogue Scale (VAS) scale rating perception of overall health and (2) 5 qualitative domains: Mobility, Self-Care, Usual Activities, Pain/Discomfort, and Anxiety/Depression.

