### 2.3.2 Secondary Endpoints

- Proportion of subjects developing AKI (any stage) based on SCr criteria from the KDIGO guideline within 7 days after T0 (AKI-SCr7d)
- Proportion of subjects developing AKI based on all captured criteria from the KDIGO guideline (i.e., AKI-SCr stage 1 to 3: increase in SCr  $\geq 0.3$  mg/dl [ $\geq 26.5$   $\mu$ mol/L] within any 48 hours, increase in SCr to  $\geq 1.5$  times baseline, and/or AKI-UO stage 2 and 3: urine volume  $< 0.5$  ml/kg per hour for 12 consecutive hours) within 72 hours after T0 (AKI-KDIGO72h)
- Proportion of subjects developing AKI based on all criteria from the KDIGO guideline within 7 days after T0 (AKI-KDIGO7d)
- Proportion of subjects with MAKE defined as all-cause mortality, RRT and/or  $\geq 25\%$  sustained reduction in eGFR based on SCr within 30 days after day of surgery (MAKE30). Sustained loss of renal function is defined as a reduction of kidney function (i.e., a reduction of eGFR of 25% or more compared to the baseline presurgery sample at visit 2) at the time of assessment (i.e., at day 30)
- Proportion of subjects with MAKE defined as all-cause mortality, RRT and/or  $\geq 25\%$  sustained reduction in eGFR based on SCr within 90 days after day of surgery (MAKE90)

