#### 5.3.1.2 Urinary Output

For randomized subjects, UO every 12 hours and total fluid intake every 24 hours will be recorded when the subject is in the ICU. During the first 72 hours following surgery (i.e., visit 3 to visit 5) the investigator will record information on AKI-UO stages 1 to 3 in the eCRF to assess their occurrence as per investigator discretion. When the subject is discharged from the ICU, but is still in the hospital, UO and fluid intake every 24 hours will be recorded up to day 7 (visit 8).

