### 6.1.2 Secondary Efficacy Endpoints

1. Proportion of subjects developing AKI (any stage) based on SCr criteria from the KDIGO guideline within 7 days after T0 (i.e., until Visit 8) (AKI-SCr7d).

[SCr evaluation visit: baseline, Visit 3, 4, 5, 6, 7 and 8 (24 hours, 48 hours, 72 hours after T0, and Day 5, 6 and 7/DoD). If the hospital discharge is earlier than Day 7, then the visits prior to DoD and Visit 8 (DoD) will be used.]

- If the subject meets at least one of the following conditions, then the subject will be treated as developing AKI-SCr7d.
  - Increasing in SCr  $\geq 0.3 \text{ mg/dL}$  within any 48 hours until Visit 8; and/or,
  - Increasing in SCr  $\geq 1.5$  times baseline until Visit 8.

2. Proportion of subjects developing AKI based on all captured criteria from the KDIGO guideline within 72 hours after T0 (AKI-KDIGO72h).

[SCr evaluation visit: baseline, Visit 3, 4 and 5 (24, 48, 72 hours after T0)]

[UO evaluation visit: Visit 3, 4, and 5 (0-12 hours, 12-24 hours, 0-24 hours, ..., and 48-60 hours, 60-72 hours and 48-72 hours after T0)]

- If the subject meets at least one of the following conditions, then the subject will be treated as developing AKI-KDIGO72h.
  - Increasing in SCr  $\geq 0.3$  mg/dL within any 48 hours until Visit 5;
  - Increasing in SCr  $\geq 1.5$  times baseline until Visit 5; and/or,
  - Urine volume  $< 0.5$  ml/kg per hour for any one of 12 consecutive hours until Visit 5 (i.e., 0-12 hours after T0, 12-24 hours after T0, ..., or 60-72 hours after T0).
- 3. Proportion of subjects developing AKI based on all criteria from the KDIGO guideline within 7 days after T0 (AKI-KDIGO7d).

[SCr evaluation visit: baseline, Visit 3, 4, 5, 6, 7 and 8(24 hours, 48 hours, 72 hours after T0, and Day 5, 6 and 7/DoD). If the hospital discharge is earlier than Day 7, then the visits prior to DoD and Visit 8 (DoD) will be used.]

[UO evaluation visit: Visit 3, 4, 5, 6, 7 and 8 (0-12 hours, 12-24 hours, 0-24 hours, ..., and 120-132 hours, 132-144 hours and 120-144 hours after T0). If the hospital discharge is earlier than Day 7, then the visits prior to DoD and Visit 8 (DoD) will be used.]

  - If the subject meets at least one of the following conditions, then the subject will be treated as developing AKI-KDIGO7d.
    - Increasing in SCr  $\geq 0.3$  mg/dL within any 48 hours until Visit 8;
    - Increasing in SCr  $\geq 1.5$  times baseline until Visit 8; and/or,

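### SAP Table 3 stages urine-output AKI on more than 12 and more than 24 hours where the protocol has at least 12 and at least 24, so an isolated 12-hour ICU block is an AKI-KDIGO event with no AKI-UO stage

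*SAP*

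**What the plan says.** **Staging rule in the SAP (Table 3, section 6.1.3).** Stage 2 is urine output below 0.5 "mL/kg per hour for over 12 hours". Stage 3 is below 0.3 "mL/kg per hour for over 24 hours, or Anuria for over 12 hours". Stage 1 on urine output is not used.

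**Staging rule in the protocol (section 2.3, Table 3).** The rates are the same, but the durations are ≥ 12 hours for stage 2, and ≥ 24 hours or anuria ≥ 12 hours for stage 3. Both tables cite the same KDIGO AKI guideline.

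**Event rule for the secondary endpoint.** Protocol 2.3.2 describes its AKI-UO stage 2 and 3 component as a volume below 0.5 ml/kg per hour "for 12 consecutive hours) within 72 hours after T0 (AKI-KDIGO72h". SAP 6.1.2 makes this below 0.5 "ml/kg per hour for any one of 12 consecutive hours until Visit 5", listing fixed blocks from 0–12 to 60–72 hours after T0. AKI-KDIGO7d continues the blocks to 132–144 hours.

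**How the data are held (protocol 5.3.1.2).** "UO every 12 hours and total fluid intake every 24 hours will be recorded when the subject is in the ICU". On the ward, "UO and fluid intake every 24 hours will be recorded up to day 7 (visit 8".

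**Where Table 3 is used.** SAP 6.1.3 items 15 and 16 ("All stages AKI-UO (AKI-UO stage 2 or stage 3", AKI-UO stage 3, and the composite of AKI-SCr stage 2 or 3 and/or AKI-UO stage 3), severity items 19 and 20, and the MAKE contingency tables in SAP 7.4.2.

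**The concern.** With continuously timed urine output, the difference between *over* 12 hours and *at least* 12 hours would rarely matter. Here the records are 12 or 24 hours long, so the boundary is met exactly, and one word decides whether a record qualifies.

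The SAP would then apply two urine-output rules to the same data: one for the AKI-KDIGO secondary endpoints and a stricter one for AKI-UO and severity. A subject could be an AKI event on urine output in one table and have no AKI in another, with nothing in the SAP to explain it. The AKI-UO proportions, and their cross-tabulation against MAKE, would also omit cases that the protocol's own staging includes.

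**Working it through.** The plan states no figure that depends on this rule, so there is none to reproduce. The check compares the rules and then counts.

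**Step 1. Which records qualify.** A run of k ICU blocks lasts 12k hours; a ward total lasts 24 hours.

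| Record, rate criterion met | Protocol Table 3 | SAP Table 3, literal |
|---|---|---|
| One ICU block, < 0.5 | stage 2 (12 ≥ 12) | none (12 is not > 12) |
| One ICU block, anuria | stage 3 (12 ≥ 12) | none |
| Two consecutive blocks, each < 0.5 | stage 2 | stage 2 (24 > 12) |
| Two consecutive blocks, each < 0.3 | stage 3 (24 ≥ 24) | stage 2 only (24 is not > 24) |
| One ward total, < 0.5 | stage 2 | stage 2 (24 > 12) |
| One ward total, anuria | stage 3 | stage 3 (24 > 12) |
| One ward total, < 0.3, not anuric | stage 3 | stage 2 only |

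So the literal SAP rule needs two blocks (24 hours) for stage 2, and three blocks (36 hours) for the < 0.3 arm of stage 3.

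**Step 2. How often the rules disagree, as logic.** Take each block as deficit or no deficit (< 0.5), for a subject in ICU throughout 0–72 hours: 2^6 = 64 patterns.
- At least one deficit block (AKI-KDIGO urine-output rule): 64 − 1 = 63.
- No two adjacent deficit blocks: 1 + 6 + 10 + 4 = 21 (zero, one, two or three deficits). At least two adjacent (literal stage 2): 64 − 21 = 43.
- AKI-KDIGO event without an AKI-UO stage: 63 − 43 = 20. With ≥ 12 hours: 63 − 63 = 0.
- Repeating the count with < 0.3 as the deficit, 43 patterns have a run of at least 24 hours and 20 a run of more than 24.

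Over 0–144 hours in 12-hour blocks, 4095 of 4096 patterns meet the event rule and 3719 meet literal stage 2: 376 disagree, and none after the correction.

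**Step 3. One subject traced through the outputs.** The 0–12 hour block is below 0.5, later output is adequate, and there is no AKI-SCr.
- AKI-KDIGO72h: event.
- AKI-UO proportion: not counted.
- Urine-output severity: no AKI.
- Most severe of SCr or urine output: no AKI. With AKI-SCr stage 1, the combined table would show stage 1, where the protocol's durations give stage 2.

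**Step 4. Illustration of size, on assumed rates.** Let p be the chance of a deficit in a block. Protocol 2.2.1 expects the subject to leave the ICU within 12 to 48 hours, that is 1 to 4 blocks. For n = 4 independent blocks:

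P(at least one) = 1 − (1−p)^4

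P(two adjacent) = 1 − [(1−p)^4 + 4p(1−p)^3 + 3p²(1−p)²]

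| Assumed p | One block enough | Two adjacent needed |
|---|---|---|
| 0.05 | 1 − 0.8145 = 0.186 | 1 − (0.8145 + 0.1715 + 0.0068) = 0.007 |
| 0.10 | 1 − 0.6561 = 0.344 | 1 − (0.6561 + 0.2916 + 0.0243) = 0.028 |
| 0.20 | 1 − 0.4096 = 0.590 | 1 − (0.4096 + 0.4096 + 0.0768) = 0.104 |

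For n = 2 and p = 0.10 the figures are 1 − 0.81 = 0.190 and 0.10² = 0.010. Low urine output tends to persist. At p = 0.10, with a 50% chance that a deficit continues into the next block (n = 4), they are 0.242 and 0.10. The gap narrows with persistence but remains.

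Steps 2 and 4 treat staging as a run of deficit blocks. SAP 6.1.2 also lists 24-hour windows such as 0–24 hours. If ICU data were also averaged over those, a very low isolated block could pull a 24-hour average below 0.5 and qualify. That would reduce the disagreement without removing it.

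**The case against.** **The intended meaning may be *at least*.** The protocol says 12-hour recording was chosen so that stages 2 and 3 could be analysed, protocol 2.3.2 equates those stages with 12 consecutive hours, and both tables cite the same guideline. The SAP revision history (version 3.00) says the AKI definition was corrected to align with that guideline and records no choice of longer durations. This is probably right about intent. But the SAP nowhere says so, and the creatinine column of the same table uses exact ≥ and < signs, so a programmer could reasonably code *over* as >.

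**A different source may supply the stages.** The investigator records AKI-UO stages 1 to 3 in the eCRF for the first 72 hours. The SAP does not say that this field determines the staging, so it does not settle the question.

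**The effect is confined to exploratory outputs.** This stands. AKI-SCr72h and the AKI-KDIGO endpoints carry their own definitions.

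**Stronger readings that the documents do not support.**
- A reader might infer that one 24-hour ward total never qualifies and two days are always needed. A 24-hour total satisfies *over* 12 hours, for stage 2 and for anuria; only the < 0.3 arm of stage 3 fails on it.
- A reader might infer that an isolated block gives no AKI in every severity table. The SCr table is untouched, and the combined table shows no AKI only if there is also no AKI-SCr. The sample-size assumption of a 60% placebo AKI proportion suggests many subjects would carry an SCr stage anyway.
- A reader might take the percentages in the working as expected undercounts. They rest on assumed rates with no source in the documents.

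**Conclusion.** The concern holds as a conflict of definitions. SAP Table 3, read as written, disagrees with protocol Table 3 and with the SAP's own AKI-KDIGO rule at exactly the durations in which urine output is recorded. An isolated 12-hour ICU block is left unstaged (including an anuric one, which the protocol places in stage 3), and exactly 24 hours below 0.3 falls short of stage 3 on that arm.

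The affected outputs are the AKI-UO proportions, the composite with AKI-UO stage 3, urine-output and combined severity, and the MAKE contingency tables using AKI-UO. No power, alpha or sample-size statement depends on it.

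In block patterns, 20 of 64 disagree over 0–72 hours. The size in patients is unknown. The conclusion assumes that *over* is coded as strictly greater than, and that staging is derived from the recorded volumes; the SAP confirms neither and excludes neither. A correction should be made because the tables may otherwise not reconcile with a secondary endpoint.

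**What to change.** In SAP Table 3, AKI-UO column, replace *over 12 hours* with ≥ 12 hours in both the stage 2 and the anuria entries, and *over 24 hours* with ≥ 24 hours, to match protocol Table 3 and SAP 6.1.2.

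At the same time, clarify the SAP 7.4.4 sentence under the 72-hour alternative AKI definitions, which says the stages are to be used for subjects developing AKI-SCr72h. Taken literally, it could leave subjects with urine-output AKI only unstaged whatever durations Table 3 uses. State that AKI-UO staging applies whether or not AKI-SCr is met, and whether it is derived from recorded volumes or from the investigator's eCRF entry.

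The cost is three small edits in one table and a sentence or two elsewhere. No new data are needed, and the primary and secondary analyses do not change. The edits should be made before database lock.

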#### Follow up

It is assumed that the subjects will be in the hospital up to at least 1 week after the surgery. On days 5, 6 and 7 after T0 (visits 6, 7 and 8, respectively), applicable assessments will be performed to assess study endpoints, including AKI (based on SCr). After end of all the procedures of visit 5, subjects can be discharged at the discretion of the investigator. If the subject is discharged before day 7, visit 8 will be done on the day of discharge and no site visits are required after discharge up to day 7. If the subject is discharged after day 7, visit 8 will be done on day 7 and no additional assessments are required after day 7 up to discharge, but the last result of SCr before discharge from local laboratory testing will be collected. Following day 7 (visit 8) or discharge, subjects will be followed up on day 30 (visit 9) and 90 (visit 10) following surgery. On visits 9 and 10 a composite endpoint of major adverse

kidney events (MAKE), including all-cause mortality, RRT and/or  $\geq 25\%$  sustained reduction in eGFR will be assessed.

Total number of hospital days and ICU days during initial hospitalization will be recorded. If the subjects are readmitted to hospital for any reason during the 90 follow-up days, the total number of hospitalizations and number of days hospitalized through day 30 and 90 will be recorded.

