### **7.11.3 Visit Windows**

All analyses will be performed based on CRF visit with the following exceptions:

- For the baseline, the value at presurgery will be used as the baseline. However in case of missing value at presurgery, the last measurement before surgery will be used as the baseline.
- For the pharmacodynamic analysis, the data for 2-4 hours postdose at visit 2 which is taken within 1 hour after the administration of study drug will be excluded for analysis.

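### If a Day 5 discharge sample is entered only as Visit 8, SAP 6.1.3 items 17 and 18 leave it out of the 5-day AKI endpoints

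*SAP*

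**What the plan says.** For the two 5-day endpoints, SAP 6.1.3 items 17 and 18 give the visit list as "SCr evaluation visit: baseline, Visit 3, 4, 5 and 6 (24 hours, 48 hours, 72 hours after T0, and Day 5". Visit 8 is not in it. The early-discharge rule reads "If the hospital discharge is earlier than Day 5, then the visits prior to DoD and Visit 8 (DoD) will be used". It appears three times: for creatinine in item 17, and for creatinine and urine output in item 18. The criteria bullets in both items stop at Visit 6.

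The protocol (2.2.1, Follow up) sets the calendar: "On days 5, 6 and 7 after T0 (visits 6, 7 and 8, respectively), applicable assessments will be performed". On early discharge it says "If the subject is discharged before day 7, visit 8 will be done on the day of discharge", and the schedule of assessments gives Visit 8 a window of 4 to 7 days. The earliest discharge is also fixed there: "After end of all the procedures of visit 5, subjects can be discharged at the discretion of the investigator".

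Two general SAP rules bear on the result. Section 7.11.3 says "All analyses will be performed based on CRF visit with the following exceptions"; the two exceptions concern the baseline value and a pharmacodynamic sample. Section 6.1.3 says of exploratory event proportions that, unless stated otherwise, "subjects whose status of events are unknown due to, e.g., missing data will not be counted as the events".

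The 7-day endpoints in SAP 6.1.2 use a parallel rule: "If the hospital discharge is earlier than Day 7, then the visits prior to DoD and Visit 8 (DoD) will be used". Visit 8 is already in their visit list.

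**The concern.** Day 5 is inside a 5-day window, so a creatinine drawn on Day 5 should count towards AKI-SCr5d whatever page it was entered on. The boundary is strict, however: a Day 5 discharge is not earlier than Day 5, so Visit 8 is not brought in. If Visit 6 is blank because the day's sample went on the Visit 8 page, the endpoint rests on Visits 3 to 5, the same post-surgery creatinine visits as AKI-SCr72h.

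At stake is the timing of a subset of events. AKI first seen on such a sample would be absent from the 5-day count and present in the 7-day count. Protocol Attachment 1 says the 5-day endpoints were added to allow comparison with a competitor's endpoint and to help choose the timing of AKI assessment in later studies. A count that depends on which page was filled in serves neither purpose well. Both endpoints also have planned CMH tests (SAP 7.4.4, Group 1) and enter the contingency tables against MAKE30 and MAKE90 (SAP 7.4.2).

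**Working it through.** The plan states no figure that depends on this rule, so there is none to reproduce. The check traces the rule through each discharge day.

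**Inputs.** Visit 5 is Day 4 (T0 + 72 hours), Visit 6 is Day 5 and Visit 7 is Day 6 (protocol Table 1). Visit 8 is the discharge day if discharge is before Day 7, otherwise Day 7. Discharge cannot precede the end of Visit 5. Items 17 and 18 use Visits 3 to 6, plus Visit 8 if the discharge day is less than 5. The condition under test is that the discharge-day sample is held as Visit 8 and Visit 6 is not separately entered on a Day 5 discharge.

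| Discharge day | Visit 6 held | Day of Visit 8 | Visit 8 used as written | Last creatinine day used, as written | Last creatinine day used, with *on or before Day 5* |
|---|---|---|---|---|---|
| 4 | no | 4 | yes | 4 | 4 |
| 5 | no (condition) | 5 | no | **4** | **5** |
| 6 | yes | 6 | no | 5 | 5 |
| 7 | yes | 7 | no | 5 | 5 |
| 8 | yes | 7 | no | 5 | 5 |

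Only the Day 5 row loses a value inside the window. If Visit 6 is also entered on Day 5, that row becomes 5 as written and there is no loss. A Day 4 discharge has no Day 5 sample to lose, so the fair contrast is with a Day 6 discharge, whose Day 5 value is used.

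Under the protocol, the exception as written can reach only Day 4 discharges. There Visit 8 falls on the same day as Visit 5 and adds little.

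**Worked example.** Take baseline 1.00, Visit 3 1.05, Visit 4 1.10, Visit 5 1.10 and a Day 5 discharge sample of 1.45 mg/dL, entered only as Visit 8.

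- To Visit 5: largest rise 1.10 − 1.00 = 0.10, below 0.3; ratio 1.10/1.00 = 1.10, below 1.5. AKI-SCr5d: no.
- With the Day 5 sample: 1.45 − 1.10 = 0.35 in about 24 hours, at least 0.3. AKI is met.
- AKI-SCr7d includes Visit 8, so the subject is an event there. Time to AKI-SCr7d (items 22 and 23: date met minus date of T0, plus 1) is 4 + 1 = 5 days. The outputs would show AKI reached on Day 5 in a subject scored as having no AKI by Day 5.

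**Scale, on assumptions only.** The documents give neither the discharge-day distribution nor the rate of AKI first met on Day 5. Suppose 10% to 30% of 110 subjects per arm leave on Day 5 and all are entered only as Visit 8: 110 × 0.10 = 11 to 110 × 0.30 = 33 subjects. Suppose 2% to 6% of these first meet AKI on that sample: 11 × 0.02 = 0.2 to 33 × 0.06 = 2.0 events per arm. This shows an order of magnitude and is not an estimate.

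**The case against.** The strongest reply is that Visit 6 need not be blank. The protocol schedules Visit 6 on Day 5 and waives site visits only after discharge, so a subject still in hospital that day is due Visit 6. Two visits on one day are already implied: a subject leaving on Day 4 must finish Visit 5 before discharge and also has Visit 8 that day. By the same logic a Day 5 discharge has both Visit 6 and Visit 8, and the strict boundary is then coherent.

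This stands to the extent that the loss is conditional. A reader might infer that every subject discharged on Day 5 loses the Day 5 creatinine. The documents do not support that, because nothing says Visit 6 is skipped or replaced, and the eCRF instructions that would settle it are not part of the plan.

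It does not remove the point. The SAP rule separates the visits before the day of discharge from Visit 8 on that day, which suggests that the discharge-day record is held as Visit 8. Item 27 likewise takes the discharge creatinine from Visit 8 when discharge is at or before Day 7. Entry on Visit 8 alone is therefore foreseeable, and the rule then gives the wrong result with nothing in 7.11.3 to rescue it.

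On urine output, the same boundary wording applies, but the documents do not show that a 72 to 96 hour record would sit under Visit 8 alone. The demonstrated gap is in creatinine.

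**Conclusion.** The point holds as a conditional, minor defect. When a Day 5 discharge sample is entered only as Visit 8, items 17 and 18 as written ignore it. With no criterion met by Visit 5, the subject is scored as no AKI-SCr5d. AKI-KDIGO5d misses the event too unless its urine-output criterion is met. AKI-SCr7d counts it.

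The reach is two exploratory endpoints and the MAKE contingency tables that use them. The primary endpoint stops at Visit 5, and the 7-day secondary endpoints include Visit 8, so neither is affected. The size cannot be computed from the documents; the 0.2 to 2.0 events per arm above rests entirely on assumed rates and on no Visit 6 entry.

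Two further inferences should be resisted. One is that the treatment comparison is biased: the rule is the same in both arms of a blinded trial, and nothing in the documents points to a differential effect. The other is that the wording was carried over from the 7-day endpoints. The rules are parallel, but the documents do not say how the text arose, and the point does not depend on it.

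**What to change.** In the creatinine rule of item 17 and the creatinine and urine-output rules of item 18, replace *earlier than Day 5* with *on or before Day 5*, so that Visit 8 (DoD) serves as the Day 5 record when Visit 6 was not separately done. In the criteria bullets of both items, replace *until Visit 6* with *until Visit 6, or Visit 8 (DoD) if discharged on or before Day 5*. Without the second change the bullets would still exclude the value that the first brings in.

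The cost is a short SAP edit in two items and the matching derivation code. No new data are needed, creatinine results for other discharge days do not change, and the rule can be written without reference to treatment. If sites did complete Visit 6 on the day of discharge, the edit is harmless. If the SAP is already final, SAP section 1 provides for recording changes that affect the analyses in the clinical study report.
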